6.3.2 Secondary Efficacy Analyses

Duration of Response (DoR)

DoR will be estimated using the Kaplan-Meier method along with the Kaplan-Meier plot if an adequate number of responses are observed to warrant.

The number and percentage of subjects who had events (response discontinued) or were censored will be summarized. The median, 25th percentile, 75th percentile, minimum and maximum will be provided along with the 95% CI for the median. The proportion and 95% CI for the number of subjects with durable responses at 6 months and 12 months from the onset of response will be provided. Other clinically relevant time points may also be included if data warrant.

Progression-free Survival (PFS)

PFS based on investigator assessments will be estimated using the Kaplan-Meier method and will be presented graphically if adequate data warrant. Censoring rules for the primary and sensitivity analyses are described in Table .

The number and percentage of subjects who had a PFS event or were censored will be summarized. The median, 25th percentile, 75th percentile, minimum and maximum will be provided along with the 95% CI for the median. The proportion and 95% CI for the number of subjects progression-free at clinically significant time points (e.g., 6 months, 12 months) from the date of the first dose will be provided. Other clinically relevant time points may also be included if data warrant.

Overall Survival (OS)

OS will be estimated using the Kaplan-Meier method along with the Kaplan-Meier plot if adequate data warrant.

The number and percentage of subjects who died or were censored will be summarized. The median, 25th percentile, 75th percentile, minimum and maximum will be provided along with the 95% CIs for the median. The proportion and 95% CI for the number of subjects alive at clinically significant time points (e.g., 6 months, 12 months) from first treatment will be provided. Other clinically relevant time points may also be included if data warrant.

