1.3. Schedule of Activities (SoA)

1.3.1. Phase 1 E-602 Monotherapy: Dose Escalation and Backfill

Study Period Phase 1 E-602 Monothera	Jy. Dose i	USCA	ıaıı	on a	ши	Dat	KIII		eatme	ent [2:	11						P	ost Tr	eatme	nt
Cycle or Visit	Screen			Су	cle 1	[1]				Сус		[1]		C	ycle	≥3	EOT [2]		low-up	
Day	-28 to -1	1	2	3	8	9	10	15	1	8	9	10	15	1	8	15			+90 D	Q3M [4]
Visit Window (days)		-	-	-	±2	-	-	±2	±2	±2	-	-	±2	±2	±2	±2	+14	±7	±7	±7
Clinical Assessments																				
Written informed consent [5]	X																			
Performance status [6]	X	X			X				X					X			X	X	X	
Concomitant medications [7]	X	X			X			X	X	X			X	X	X	X	X	X	X	
Height (cm)	X																			
Weight (kg) [8]	X	X			X			X	X	X			X	X	X	X	X			
Vital signs/oxygen saturation [9]	X	X			X			X	X	X			X	X	X	X	X	X	X	
Medical history [10]	X																			
Adverse event assessment		X			X			X	X	X			X	X	X	X	X	X	X	
12-lead ECG	X																			
Study Treatment																				
E-602 administration		X			X			X	X	X			X	X	X	X				
Laboratory Tests																				
Coagulation [11]	X																			
Urinalysis [11]	X	X							X					X			X			
Chemistry [11]	X	X			X			X	X	X			X	X	X	X	X			
Hematology [11]	X	X			X			X	X	X			X	X	X	X	X			
Thyroid panel [11]	X	X												X						
Plasma for PK analysis [12]		X	X	X	X			X	X	X	X	X	X	X	X		X	X		
Plasma for ADA [13]		X							X					X			X	X		
Pregnancy test [14]	X	X							X					X						
Disease Assessments																				
Physical examination [15]	X	X							X					X			X			
Radiology examination [16]	X													X			X			
Pharmacodynamics and Biomarkers [17]																				
Immune cell desialylation, content and activation status by FACS		X	X	X	X	X	X	X												
Immune cell gene expression profiling (RNAseq)		X	X	X	X	X	X	X												

Study Period		Treatment [21]															Post Treatment			
Cycle or Visit	Screen		Cycle 1 [1] Cycle 2 [1] Cycle ≥3										≥3	EOT [2]	Follow-up [3]					
Day	-28 to -1	1	2	3	8	9	10	15	1	8	9	10	15	1	8	15		+30D	+90D	Q3M [4]
Visit Window (days)		-	-	-	±2	-	-	±2	±2	±2	-	-	±2	±2	±2	±2	+14	±7	±7	±7
Cytokine panels and C3a		X	X	X	X	X	X	X												
Glycoproteomic profiling		X	X	X	X	X	X	X												
Disease biomarkers [18]		X																		
Circulating tumor DNA analysis [19]		X												X						
Archival Tumor biopsy [20]	X																			
Fresh Tumor biopsy [20]	X								X											
Post-treatment Follow-up																				
Subject Contact [4]																				X

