- 16. Radiology examination of tumors includes contrast-enhanced CT (preferred) or MRI imaging of the chest, abdomen, and pelvis. The same method (CT, PET/CT, MRI) and the same technique should be used to characterize each identified and reported lesion at screening and during the study. Radiology examinations will be performed during screening (permitted up to 35 days prior to Cycle 1, Day 1), 9 weeks (±1 week) after the first dose and every 9 weeks (±1 week) thereafter, regardless of any study treatment(s) delay. An EOT examination should be performed unless the subject already has radiographic confirmation of PD ≤4 weeks prior to the EOT visit. For ovarian cancer subjects, at each radiology examination, CA-125 should also be tested.
- 17. See Section 8.5 for further information on sample collection and analyses.
- 18. Biomarkers of disease may be performed up to 72 hours prior to Day 1 as follows: carcinoembryonic antigen (CEA) and CA-125 for subjects with NSCLC, CEA and CA19-9 for subject with colorectal or pancreatic cancer, and CA-125 for subjects with ovarian cancer.
- 19. Circulating tumor DNA samples will be collected with radiological assessments. See Footnote 16.
- 20. Tumor biopsy is optional at screening and on Cycle 2 Day 1 (+4 days) during Phase 1. An archive tissue sample is required for all subjects. See Section 8.5.3 for further information.
- 21. Dosing visits should not be skipped due to dose delays.

1.3.2. Phase 1 Combination Dose Escalation and Backfill; Phase 2 E-602 Monotherapy and Combination

1.3.2. Phase 1 Combination Do	ose Escala	tion a	nd E	Back	fill; I	Phase	e 2 E	-602	Mo	notl	1er	apy	and	l Co	mb	inatio	n		
Study Period						7	Γreat	ment	[21]								ost Tr	eatme	at
Cycle or Visit	Screen			Cycle	1 [1]				Cycl	Cycle 2 [1]			Cycle ≥3			EOT [2]			
Day	-28 to -1	1	2	3	8	9	15	1	8	9	10	15	1	8	15		+30D	+90D	Q3M [4]
Visit Window (days)		-	-	-	±2	-	±2	±2	±2	-	-	±2	±2	±2	±2	+14	±7	±7	±7
Clinical Assessments																			
Written informed consent [5]	X																		
Performance status [6]	X	X			X			X					X			X	X	X	
Concomitant medications [7]	X	X			X		X	X	X			X	X	X	X	X	X	X	
Height (cm)	X																		
Weight (kg) [8]	X	X			X		X	X	X			X	X	X	X	X			
Vital signs/oxygen saturation [9]	X	X			X		X	X	X			X	X	X	X	X	X		
Medical history [10]	X																		
Adverse event assessment		X			X		X	X	X			X	X	X	X	X	X	X	
12-lead ECG	X																		
Study Treatment																			
E-602 administration		X			X		X	X	X			X	X	X	X				

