The dose for E-602 in the combination therapy cohorts will be initiated at dose level(s) that have previously completed dosing and DLT assessments (Cycle 1) as monotherapy.

Dose modifications will be made according to Section 6.5.

Phase 2 Treatment (Planned):

Subjects in Phase 2 will receive the following treatment:

Cohort	Number of Subjects	Advanced Disease	Dose of E-602	Frequency of E-602	Dose of Cemiplimab	Frequency of Cemiplimab
201	16 – 31	melanoma	monotherapy RP2D	once a week	n/a	n/a
202	16 – 31	NSCLC	monotherapy RP2D	once a week	n/a	n/a
203	16 – 31	TBDa	monotherapy RP2D	once a week	n/a	n/a
211	16 – 31	melanoma	combination RP2D	once a week	350 mg	once every 3 weeks
212	16 – 31	NSCLC	combination RP2D	once a week	350 mg	once every 3 weeks
213	16 – 31	TBDa	combination RP2D	once a week	350 mg	once every 3 weeks

^a The third cohort will treat subjects with one of ovarian, colorectal, pancreatic, breast, gastric/EGJ, head and neck or urothelial cancers, based on available data including the Phase 1 results.

The maximum duration of treatment for each subject will be 1 year, regardless of treatment delays. See Section 7.1 for early treatment discontinuation criteria.

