8.1. Efficacy Assessments

Planned timepoints for all efficacy assessments are provided in the SoA.

Subjects will undergo radiological tumor assessment at baseline during screening (up to 35 days prior to Cycle 1, Day 1), 9 weeks (± 1 week) after the first dose and every 9 weeks (± 1 week) thereafter regardless of treatment delays until the EOT visit. An examination at EOT visit should be performed unless the subject already has radiographic confirmation of PD within 4 weeks of the EOT visit.

Tumor assessment should include contrast-enhanced computed tomography (CT, preferred) or magnetic resonance imaging (MRI) of the chest, abdomen, and pelvis. The same method (positron emission tomography [PET]/CT, MRI, or CT) and the same technique should be used to characterize each identified and reported lesion throughout the study. Lesions in a previously irradiated field may be assessed as target lesions if progression since irradiation has been demonstrated.

Response to treatment will be evaluated using the RECIST version 1.1 (Eisenhauer 2009) and iRECIST (Seymour 2017). Subject responses will be classified as progressive disease (PD), stable disease, partial response (PR), and complete response (CR). A per timepoint response of Stable Disease requires a minimum of 56 days between two measures. To assess a Best Overall Response (BOR) of CR or PR per RECIST version 1.1, confirmation of the CR or PR is required at the subsequent timepoint at least 4 weeks later.

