Subjects will undergo radiological tumor assessment at baseline during screening (up to 35 days prior to Cycle 1, Day 1), 9 weeks (± 1 week) after the first dose and every 9 weeks (± 1 week) thereafter regardless of treatment delays until the End of Treatment (EOT) visit. An examination at EOT visit should be performed unless the subject already has radiographic confirmation of progressive disease (PD) within 4 weeks of the EOT visit. Response to treatment will be evaluated using the Response Evaluation Criteria in Solid Tumors (RECIST) Version 1.1 and Immunotherapy Response Evaluation Criteria in Solid Tumors (iRECIST).

The study schema is provided in Figure 1.

Figure 1 Study Schema

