6.1 General Statistical Considerations

In general, all analyses will be summarized by dose level and study treatment (e.g. monotherapy, combination with cemiplimab). Safety analysis will be based on the safety analysis population. The primary efficacy analysis will be based on the efficacy evaluable population by study treatment and/or tumor indication.

For each tumor indication, subjects administered the same study treatment may be combined for analysis purposes, regardless of study phase. Statistical inference, when performed, will be assessed at the 2-sided nominal 5% significance level without multiplicity adjustment. Point estimates will be accompanied by 95% confidence intervals (CIs). For the ORR endpoint assessed per the Simon's 2-stage design, the 2-sided 80% CI may be used.

For continuous variables, the number of observations (n), mean, standard deviation, median, minimum, and maximum will be provided as summary statistics. The mean and median will be reported to one additional decimal place compared to the original data. The standard deviation will be reported to two additional decimal places compared to the original data and the minimum and maximum will be reported to the same number of decimal places as the original data.

For categorical variables, the frequency and percentage in each category will be displayed. Percentages (e.g., for AEs and concomitant medications) will be calculated out of the population total for each cohort. Footnotes will clarify the denominator used in each output if other than the analysis set stated in the title. Percentages will be reported to one decimal place throughout unless the percentage is 100 (in which case no decimal places will be presented) or if the frequency count is zero (in which case no percentage will be presented).

For time to event data, unless otherwise noted, the median value, 25th percentile and 75th percentile will be calculated using the Kaplan-Meier method. The Brookmeyer and Crowley method will be used to calculate the CI of the median value (Brookmeyer and Crowley 1982). Also, the Greenwood formula will be used to calculate the CI of the rate of interest pertaining to the time to event data, at a given time point estimated using the Kaplan-Meier method (Kalbfleisch and Prentice 2002). The time to event analysis will be calculated only if an adequate number of responses are observed to warrant.

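### SAP 6.3.2 promises a 12-month durable-response proportion, but scheduled scans stop at end of treatment and can show at most about 10.2 to 10.6 months of response.

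*SAP*

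**What the plan says.** SAP 6.3.2 plans a Kaplan-Meier analysis of DoR and commits to the proportion, with 95% CI, of "durable responses at 6 months and 12 months from the onset of response will be provided". The analysis is conditional: SAP 6.3.2 offers the estimate and the "Kaplan-Meier plot if an adequate number of responses are observed to warrant", and SAP 6.1 adds "The time to event analysis will be calculated only if an adequate number of responses are observed to warrant". Both conditions concern the number of responses.

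The imaging schedule is set elsewhere. Protocol 8.1 puts the first on-study scan at 9 weeks (±1 week) and repeats it every 9 weeks "thereafter regardless of treatment delays until the EOT visit". SAP 2.1 agrees: "thereafter regardless of treatment delays until the End of Treatment (EOT) visit". Footnote 16 of the Schedule of Activities (SoA) says only "thereafter, regardless of any study treatment(s) delay" and names no stop, but the radiology row of the grid marks nothing after EOT.

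Protocol 6.1 fixes the upper end: "The maximum duration of treatment for each subject will be 1 year, regardless of treatment delays". SoA footnote 2 places EOT for one-year completers within 14 days of the last dose, and the grid gives the EOT visit a window of +14 days.

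Under SAP 4.2, a DoR event is radiographic progression by RECIST v1.1 or death. Responders with neither are censored at their last tumor assessment.

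**The concern.** DoR runs from the first documented response, but the imaging that measures it is anchored to first dose and ends at about one year. Roughly the first two months pass before any response can be documented, so the time left is shorter than the 12-month landmark. A responder still in response at EOT is censored before month 12 unless somebody orders an unscheduled scan.

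At stake is a figure that the plan says will be delivered but that the design cannot reliably support. Deaths still count as DoR events after scanning stops, while continuing responses are no longer observed. A 12-month value that does appear may therefore rest on a selected few subjects.

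**Working it through.** The documents state no maximum observable DoR, so there is no plan figure to reproduce. The check is date arithmetic with the SAP's own formulas.

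**Inputs**
- Earliest on-study scan: week 9 − 1 = week 8 = day 56 (Protocol 8.1).
- Last scheduled scan, at EOT for a one-year completer: day 365 if EOT coincides with the end of the treatment year; day 365 + 14 = 379 using footnote 2; day 379 + 14 = 393 only if the grid's +14-day window is added on top.
- SAP 4.2: DoR (days) = end date − first response date + 1; months = 12 × days / 365.25.

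**Longest DoR on scheduled scans, onset on day 56**

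| EOT scan | Days | Months |
|---|---|---|
| day 365 | 365 − 56 + 1 = 310 | 10.2 |
| day 379 | 379 − 56 + 1 = 324 | 10.6 |
| day 393 (both allowances) | 393 − 56 + 1 = 338 | 11.1 |

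A response first seen at the week-18 scan (earliest day 119) can show 8.1, 8.6 or 9.0 months on the same three EOT dates.

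**Latest onset that reaches a landmark** (EOT day − days needed + 1)
- 12 months needs 366 days, since 12 × 365 / 365.25 = 11.99 and 12 × 366 / 365.25 = 12.02. Latest onset is day 0, 14 or 28, in each case before the first scan is possible.
- 6 months needs 183 days (12 × 183 / 365.25 = 6.01). Latest onset is day 183 or 197, or 211 with both allowances. This landmark is reachable.

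**What the 12-month Kaplan-Meier value then is.** With ongoing responders censored by month 11.1 at the latest, there are three outcomes:
1. Non-estimable: the longest observation is censored before month 12.
2. Exactly 0: every responder still under observation has failed.
3. Set by the few subjects whose observed time passes month 12 through a late death or an unscheduled scan.

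**How often.** The documents give neither responder numbers nor durability, so these are assumptions: onset at scan 1, 2 or 3 in 60, 30 and 10%; exponential DoR; 10% of events are deaths without progression; median survival after progression 6 or 12 months; EOT scan on day 379; deaths known to month 15.

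| Responders | True 12-month durability | Non-estimable |
|---|---|---|
| 3 | 10 to 20% | about 34 to 56% |
| 6 | 10 to 20% | about 53 to 73% |
| 6 or 12 | 40 to 60% | about 84 to 94% |

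Small counts are realistic. Under SAP 2.3, 2 of 16 opens Stage 2, and the 10% null rate in 31 subjects is about 3 responders (0.10 × 31 = 3.1).

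**The case against.** **The analysis is already conditional.** It is, but on the number of responses. Twelve responders would still all be scanned on a schedule ending at EOT. The condition does not address length of follow-up.

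**Footnote 16 could mean that scanning continues after EOT.** If it did, a week 63 (±1) scan on day 434 to 448 would give 379 to 393 days (12.5 to 12.9 months) from a day-56 onset. Protocol 8.1 and SAP 2.1 both name EOT as the stop, and the grid marks no later scan, so the documents do not support that reading.

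**Other data reach past EOT.** This is partly right. Disease-status contacts run to month 15, about day 456.6, which is up to 13.2 months from a day-56 response. SAP 6.3 admits unscheduled scans, and deaths count. A reader might infer that no 12-month DoR can ever be recorded; that goes too far. But a contact schedules no scan and does not meet the radiographic definition of progression, and unscheduled scans and late deaths are not uniform across responders.

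**A non-estimable cell declares itself.** This stands for the first outcome and limits the harm. It does not cover the second and third, where a number is printed.

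**A reader might infer that the value will nearly always be non-estimable.** The documents do not support that. The highest percentages need high durability; with few responders and low durability, non-estimable results fall to about a third.

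**A reader might also infer that a primary endpoint is compromised.** SAP Table 2 lists DoR among the Phase 2 primary endpoints, but SAP 4.2 and 6.3.2 define and analyse it as secondary. The Stage 1 and final rules in SAP 2.3 use response counts only.

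**Conclusion.** The mismatch is real. On scheduled scans the longest observable DoR is 10.2 to 10.6 months. The 11.1-month figure needs two 14-day allowances that are more plainly read as one. Every reading of the EOT date falls short of 12 months, and this conclusion rests only on dates in the documents.

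The frequency of non-estimable results, from roughly one third (3 responders, 10% durability) to over 90% (at 60% durability), rests on assumed inputs and should be read as a range.

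The consequence is limited to descriptive reporting of DoR. No go/no-go rule, sample size or error rate depends on the 12-month figure. The change should be made because the plan commits to a result that its imaging schedule cannot support and that can mislead when it appears.

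**What to change.** In SAP 6.3.2, delete the 12-month DoR landmark and keep the 6-month one. The latter can be observed on scheduled scans for responses first documented by about day 183 to 197. Show numbers at risk with the Kaplan-Meier DoR curve, so that the reader can see where scheduled observation runs out.

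A ban on Kaplan-Meier estimates beyond the imaging window is not needed. The window differs by subject with the date of onset, so there is no single cut-off, and a ban would conflict with SAP 6.3, which includes unscheduled assessments.

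The cost is one clause deleted and one reporting sentence added. No scans are added, no visit changes, and the only figure lost is one that the schedule cannot deliver.

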6.4 Safety Analyses

Safety will be assessed based on reported AEs, clinical laboratory evaluations, vital signs, physical examinations, and ECOG performance status. Treatment exposure, concomitant medications, and concomitant medical procedures will also be summarized.

The safety analysis will be based on the Safety Population and will be presented by dose and study treatment, respectively. In addition, safety analyses pooling from all phases of the study (monotherapy or combination therapy) may be provided.

6.4.1 Treatment Exposure

Descriptive statistics will be provided for treatment duration (days), number of doses, cumulative dose administered, and relative dose intensity for E-602 and cemiplimab, respectively. The number and percentage of subjects with dose interruption will be summarized. The reasons for dose modifications will also be tabulated.

6.4.2 Adverse Events

All TEAEs will be summarized. For subjects who are still on study treatment, all TEAEs reported up to the data cutoff date will be included.

AEs with incomplete start date will be considered treatment emergent if:

- Day and month are missing, and the year is equal to or after the year of the first dose date of study treatment;
- Day is missing and the year is after the year of the first dose date of study treatment;
- Day is missing and the year is equal to the year of the first dose date of study treatment and the month is equal to or after the year of the first doe date of study treatment;
- Year is missing; or
- Start date is completely missing.

However, if the end date of the AE is before the first dose date of study treatment, the AE will not be treatment emergent regardless of the completeness of its start date. AEs reported in the CRF but not considered TEAEs will be listed.

All TEAEs and SAEs will be coded using the most current version of MedDRA and graded by the Investigator according to the NCI CTCAE v5.0. Frequencies and percentage of subjects reporting each PT will be presented by SOC and PT. For each subject, multiple events of the same PT will be counted once in the summary. For summaries involving severity, the worst grade among events of the same PT will be used. The following summary tables of subject incidence will be provided by study treatment:

- All TEAEs
- SAEs
- Treatment-related TEAEs
- Treatment-related TEAEs by Severity
- Treatment-related SAEs by Severity
- TEAEs by Maximum Severity
- SAEs by Severity
- Treatment-related SAEs by Severity
- Treatment-related SAEs
- SAEs leading to treatment discontinuation (E-602, cemiplimab, E-602 in combination with cemiplimab)
- TEAEs leading to treatment discontinuation (E-602, cemiplimab, E-602 in combination with cemiplimab)
- TEAEs leading to dose interruptions (E-602, cemiplimab, E-602 in combination with cemiplimab)

• TEAEs leading to study drug delays (E-602, cemiplimab, E-602 in combination with cemiplimab)

The summary tables will include SOC and PT, and where applicable, severity grade will be added. An overall summary table with the number and percentage in the major AE categories listed above will also be provided.

Listings of TEAEs, fatal TEAEs, SAEs, and TEAEs leading to treatment discontinuation will be provided. For subjects treated in Phase 1 Dose Escalation, DLTs, if any, will be listed.

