4.3 Safety Endpoints

Treatment-Emergent Adverse Events (TEAEs)

Adverse events (AE) will be coded using the Medical Dictionary for Regulatory Activities (MedDRA) dictionary v24.1 or later. Severity will be graded according to the National Cancer Institute (NCI) Common Terminology Criteria for Adverse Events (CTCAE) v5.0. All AEs, complaints, or symptoms that occur from the time of written informed consent

through the 90-day safety follow-up are to be recorded on the appropriate case report form (CRF).

A TEAE is any adverse event with an onset date on or after the date of first dose of study treatment through 90-day safety follow-up or the initiation of new anti-cancer therapy, whichever is earlier. TEAEs will be summarized in the safety analysis.

Dose-Limiting Toxicities (DLTs)

A dose-limiting toxicity (DLT) is defined as the occurrence of any of the events listed in Section 4.1.5 of the protocol that are assessed by the investigator to be possibly, probably, or definitely related to study treatment. The DLT window of observation for the purposes of dose escalation will be Cycle 1 defined as a subject receiving 3 doses of E-602 for monotherapy cohorts and 3 doses of E-602 and 1 dose of cemiplimab for combination therapy cohorts.

Exposure to Treatment

Exposure to E-602 and cemiplimab will be summarized separately. The following variables will be derived for each drug.

Total Treatment Duration will be calculated as:

Total Treatment Duration (days) = Date of Last Dose – Date of First Dose + 1

Total Treatment Duration (months) = $12 \times \text{Total Treatment Duration (days)}/365.25$

Actual Dose Administered (mg) will be calculated as:

Actual Dose Administered (mg) = Actual Cumulative Dose Administered up to the Date of Last Dose

Relative Dose Intensity (RDI) is the percentage of actual dose administered relative to the cumulative dose planned through to treatment discontinuation.

RDI will be calculated as follows:

$$RDI = 100\% x (d/D)$$

where d (mg) is actual total dose administered and D (mg) is cumulative dose planned. D is the cumulative dose that would be administered if there were no modification to dose or schedule.

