5.3 Handling of Missing Data

In general, missing data will not be imputed. Incomplete dates (missing day or month) associated with AE and concomitant medication dates may be imputed.

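### The SAP's partial-date rule for treatment-emergent AEs compares the onset month with the year of first dose, so it is wrong as written for AEs with a known month, a missing day and onset in the first-dose year

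*SAP*

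**What the plan says.** SAP 4.3 gives the governing definition: "A TEAE is any adverse event with an onset date on or after the date of first dose of study treatment", with an upper limit at the 90-day safety follow-up or the start of new anti-cancer therapy.

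SAP 6.4.2 then says which AEs with an incomplete start date are treated as emergent:

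- First bullet: "Day and month are missing, and the year is equal to or after the year of the first dose date of study treatment".
- Second bullet: "Day is missing and the year is after the year of the first dose date of study treatment".
- Third bullet: "Day is missing and the year is equal to the year of the first dose date of study treatment", together with the further condition that "the month is equal to or after the year of the first doe date of study treatment".
- The last two bullets count an AE as emergent when the year, or the whole start date, is missing.

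An override follows: "if the end date of the AE is before the first dose date of study treatment, the AE will not be treatment emergent". AEs that are not classed as emergent leave the TEAE tables: "AEs reported in the CRF but not considered TEAEs will be listed".

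SAP 5.3 adds only that "Incomplete dates (missing day or month) associated with AE and concomitant medication dates may be imputed". It gives no algorithm. Protocol 9.2.4.2 defines TEAEs by onset date and does not deal with partial dates.

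**The concern.** The third bullet is the only rule written for an AE whose month and year are known, whose day is missing, and whose year is the first-dose year. Its first half has already matched the years. The second half should therefore compare months, but it names the year again.

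One literal reading produces an odd ordering. Suppose first dose was in March 2023. An AE dated only 2023 is emergent under the first bullet, while an AE dated May 2023, which is certainly after first dose, would fail the third. The better-dated event would be treated worse.

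The rule feeds AE incidence, a primary endpoint in Phase 1 and a secondary endpoint in Phase 2. Treatment lasts at most one year, so for many subjects much of the AE period falls in the first-dose calendar year. AEs are also collected from consent, so pre-dose events will be in the database and the rule has to separate them from post-dose events.

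**Working it through.** The plan states no figure that depends on this rule, so there is nothing to reproduce. The check enumerates the cases.

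**Inputs.** First-dose year Y, first-dose month m0 (1 to 12), and onset month m (1 to 12) in the same year Y. The day is missing and no end date falls before first dose. The bullets are those of SAP 6.4.2, and the definition is that of SAP 4.3.

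**Cases.** 12 × 12 = 144 month pairs:

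- onset month later than first-dose month: (12 × 11)/2 = 66 pairs
- same month: 12 pairs
- onset month earlier: (12 × 11)/2 = 66 pairs
- check: 66 + 12 + 66 = 144

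**Three readings of the third bullet.**

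- A, numbers: emergent if m ≥ Y. The largest m is 12, which is below any calendar year, so this is always false.
- B, calendar time: emergent if the year containing month m is equal to or after Y. The years already match, so this is always true.
- C, month against month: emergent if m ≥ m0.

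| Reading | Later month (66) | Same month (12) | Earlier month (66) | Total emergent |
|---|---|---|---|---|
| A | 0 | 0 | 0 | 0 |
| B | 66 | 12 | 66 | 144 |
| C | 66 | 12 | 0 | 78 |

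**Comparison with the definition.** Under SAP 4.3 the 66 later-month pairs are emergent and the 66 earlier-month pairs are not, whatever the missing day. The 12 same-month pairs cannot be decided without the day. Reading A misses all 66 clear post-dose pairs. Reading B includes all 66 pre-dose pairs. Reading C agrees with the definition on all 132 decidable pairs (66 + 66). It counts the 12 open pairs as emergent, in line with the inclusive approach of the neighbouring bullets.

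**Scope.** If the month is missing too, the first bullet makes a first-dose-year AE emergent under every reading. If the year is later, the second bullet does. Only AEs with a known month, a missing day and onset in the first-dose year are affected.

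**Meaning of the counts.** The 144 pairs cover the possible cases; they are not equally likely. Screening runs up to 28 days before dosing, so a pre-dose AE would ordinarily carry the first-dose month or the month just before it. One that ended before first dose is removed by the override.

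**Size in one table row.** If one subject changes status, incidence moves by 1/3 = 33 percentage points in a cohort of 3, 1/6 = 17 points in a cohort of 6, and 1/15 = 6.7 points in a cohort backfilled to the maximum of 15. These are upper illustrations: they require that the subject has no other AE counted in that row, because repeated events of one preferred term count once.

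**The case against.** The strongest reply is that the definition in SAP 4.3 already settles most cases. An onset in a later month is after first dose and an onset in an earlier month is before it, so 132 of the 144 pairs are decided and only the 12 same-month pairs are open. The bullets say which AEs are emergent; they do not say that an AE failing every bullet is non-emergent even when it plainly meets the definition. The slip is evident (the same line misspells dose), and partial dates may be imputed before the rule is applied.

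Much of this stands. A reader might infer that the condition can never be met, that such AEs are lost, and that incidence is understated. The documents do not support that: it follows from reading A only, and reading B errs in the opposite direction. A reader might also take every first-dose-year AE with a missing day to be affected. The first bullet rules that out when the month is missing as well. Nor does the error reach dose escalation, because DLTs have their own Cycle 1 definition in SAP 4.3 and protocol 4.1.5.

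The reply does not make the bullet correct. It is the text written for exactly this case, and neither reading of it agrees with SAP 4.3. Imputation is optional and has no stated method. The definition alone also leaves the same-month cases undecided, and these include events soon after the first dose.

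**Conclusion.** The third bullet is wrong as written and needs correcting, but the point is minor. It leaves one class of AE with a rule that yields 0 or 144 emergent pairs out of 144, depending on how it is read, where month against month yields 78. Under-counting and over-counting are both possible, and neither is established.

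The documents do not say how many AEs have a missing day. If 2% to 5% did, which is an assumption with no source in the documents, the affected share would be limited to those that also have a known month and onset in the first-dose year. If the programmer corrects the slip from context, the effect is nil. AEs not classed as treatment-emergent would still appear in a listing.

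**What to change.** In the third bullet of SAP 6.4.2, replace the word year in the second comparison with month, so that the onset month must be equal to or after the month of the first dose date, and correct the misspelling of dose in the same line. The other bullets and the end-date override can stay as they are.

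The cost is one word in the SAP, preferably before the TEAE derivation is programmed. No change to data collection, sample size or the protocol is needed.
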